Recent experimental works reveal that the dopaminergic (DA) system may well be involved in the occurrence of cognitive decline, often being predictive of rapidly progressive forms of Alzheimer's disease (AD). In association to cognitive decline symptoms about 35-40% of AD patients present with extrapyramidal signs, supporting the idea that DA-containing neurons undergo degenerative changes. In AD, neurons forming the nigrostriatal pathway show several pathologic changes like neurofibrillary tangles, A\beta plaques, neuropil threads, neuronal loss and also decrease in DA content, all changes suggesting the clear involvement of DA in the pathophysiology of cognitive decline and non-cognitive symptoms of AD. Reduced expression of both subtypes of DA receptors, D1-like and D2-like has been observed in prefrontal cortex and in hippocampus of AD patients. Interestingly, although the dorsal striatum is relatively spared in AD, its ventral homologous, the nucleus accumbens, is highly affected. Furthermore, recent imaging studies showed atrophy of this nucleus in a cohort of late onset AD patients, but not in the early-onset AD patients. Recent works from our group showed surprising positive effects of DA drugs on cortical neurotransmission, synaptic plasticity mechanisms and also on cognitive performances, suggesting a possible therapeutic effects for these drugs in the treatment of AD. The primary objective of this protocol is to verify the efficacy on cognition and overall clinical response of dopaminergic-agonist rotigotine, a cognitive enhancer that improves cholinergic activity and cortical plasticity, in patients with mild AD. Specifically, the main aim is to determine if treatment with a common FDA-approved dopaminergic agonist-rotigotine, as add-on therapy to cholinesterase inhibitors treatment (donepezil or rivastigmine), can improve cognitive abilities and modify physiological cortical activity in patients with mild AD. Rotigotine treatment in add-on therapy was used in our previous experience (Koch et al., 2014), and was well tolerated by patients with no side effects. To test if rotigotine changes brain physiology, we will use neurophysiological tools such as transcranial magnetic stimulation and electroencephalography to measure changes in cortical activity. This is a phase IIa 24-week,

prospective, randomized, double-blind placebo controlled study. The study is designed to evaluate the efficacy, safety, and tolerability of transdermal patch of Rotigotine (RTG) versus placebo (PLC) as add-on therapy with AChEI in patients with mild AD according to the consensus diagnostic criteria and MMSE score of ≥18 and ≤24 at screening. Two groups of patients with mild AD will be involved (50 patients each). One group will be assigned to treatment with RTG 4 mg and the other one to PLC as add on to AChEI therapy. Clinical and neurophysiological measurements will be collected before and after drug administration.

120 SECTION 3. ABBREVIATIONS AND DEFINITIONS

- 121 **A** β : amyloid- β peptides
- 122 **AChEI:** acetylcholinesterase inhibitor
- 123 **AD:** Alzheimer's disease
- 124 ADAS-Cog: Alzheimer's Disease Assessment Scale—Cognitive subscale
- 125 ADCS-ADL: Alzheimer's Disease Cooperative Study–Activities of Daily Living Inventory
- **ADDF:** Alzheimer's Drug Discovery Foundation
- 127 AE: adverse event: Any untoward medical occurrence in a patient or clinical investigation subject
- administered a pharmaceutical product that does not necessarily have a causal relationship with this
- treatment. An adverse event can therefore be any unfavorable and unintended sign (including an abnormal
- laboratory finding), symptom, or disease temporally associated with the use of a medicinal (investigational)
- product, whether or not related to the medicinal (investigational) product.
- 132 **ANOVA:** analysis of variance
- 133 **APOE:** apolipoprotein E
- 134 Blinding: A procedure in which one or more parties to the trial are kept unaware of the treatment
- assignment(s). Blinding will remain in effect until final database lock. A double-blind study is one in which
- neither the patient nor any of the investigator who are involved in the treatment or clinical evaluation of the
- subjects are aware of the treatment received.
- 138 **CDR:** Clinical Dementia Rating Scale
- 139 CRF: Case report form, a printed or electronic form for recording study patients' data during a clinical
- study, as required by the protocol.
- 141 **CSF:** cerebrospinal fluid
- 142 DA: dopamine
- 143 **EEG:** electroencephalogram
- 144 Efficacy: Efficacy is the ability of a treatment to achieve a beneficial intended result under controlled
- 145 conditions.
- End of study (trial): The date of the last visit or last scheduled procedure shown in the Study. Schedule for
- the last active patient in the study.
- 148 **FAB:** Frontal assessment battery
- 149 GABA: Gamma-Aminobutyric acid
- 150 **GLMM:** Generalized Linear Mixed Model
- 151 **Informed consent:** A process by which a patient voluntarily confirms his or her willingness to participate in
- a particular trial, after having been informed of all aspects of the trial that are relevant to the patient's
- decision to participate. Informed consent is documented by means of a written, signed, and dated informed
- consent form.
- 155 **Intent-to-Treat (ITT):** The principle that asserts that the effect of a treatment policy can be best assessed by
- evaluating on the basis of the intention to treat a patient (that is, the planned treatment regimen) rather than

- the actual treatment given. It has the consequence that patients allocated to a treatment group should be
- 158 followed up, assessed, and analyzed as members of that group, irrespective of their compliance to the
- planned course of treatment.
- **Investigational product:** A pharmaceutical form of an active ingredient or placebo being tested or used as a
- 161 reference in a clinical trial
- **Investigator:** A person responsible for the conduct of the clinical study at a study site. If a study is
- 163 conducted by a team of individuals at a study site, the investigator is the responsible leader of the team and
- may be called the principal investigator
- 165 IRB/ERB: Institutional Review Board/Ethical Review Board: a board or committee (institutional, regional,
- or national) composed of medical professional and nonmedical members whose responsibility is to verify
- that the safety, welfare, and human rights of the patients participating in a clinical study are protected.
- 168 MMSE: Mini-Mental State Examination
- 169 NINCDS/ADRDA: National Institute of Neurological and Communicative Disorders and
- 170 Stroke/Alzheimer's Disease and Related Disorders Association
- 171 **NPI:** Neuropsychiatric Inventory
- 172 Patient: A study participant who has the disease or condition for which the investigational product is
- targeted.

188

- 174 **PFC:** dorsolateral prefrontal cortex
- 175 **SAP:** statistical analysis plan
- 176 Study Entry Terms:
- 177 1) Screen: The act of determining if an individual meets minimum requirements to become part of a pool of
- 178 potential candidates for participation in a clinical study. In this study, screening involves medical and
- 179 neurological tests, including magnetic resonance imaging or computed tomography, and lumbar puncture for
- 180 CSF biomarkers analysis for diagnostic purposes.
- 181 2) Enroll: The act of assigning a patient to a treatment. Patients who are enrolled in the study are those who
- have been assigned to a treatment.
- 183 3) Enter: The act of obtaining informed consent for participation in a clinical study from patients deemed
- eligible or potentially eligible to participate in the clinical study. Patients entered into a study are those who
- sign the informed consent form directly or through their legally acceptable representatives.
- **TMS:** Transcranial Magnetic Stimulation.

SECTION 4: STUDY RATIONALE

190

191

192

193

194

195

196

197

198

199

200

201

202

203

204

205

206

207

208

209

210

211

212

213

214

215

In recent years several evidences suggested that the impairment of synaptic plasticity represents a pathogenic key in developing AD. Dopamine (DA) is a key neuromodulator affecting several distinct steps of synaptic transmission, including the probability of neurotransmitter release, the post-synaptic sensitivity to neurotransmitter, and the membrane excitability of the pre- and postsynaptic cells. From a cognitive perspective, DA is known to play an important role in the control of high cognitive functions such as memory, learning, attention and decision making. There is experimental evidence demonstrating that in the cerebral cortex, as well as in the basal forebrain, DA modulates the activity not only of pyramidal cells and GABA interneurons, but also of diffuse cholinergic projections from neurons located in the basal forebrain (Goldman-Rakic et al., 1999, and 2000; Paspalas et al., 2005; Berlanga et al., 2005; Zhang et al., 2009). Notably, the dysfunction of dopaminergic transmission has been hypothesized as a new player in the pathophysiology of Alzheimer's disease (Itoh et al., 1996; Joyce et al., 1998; Kemppainen et al., 2003; Kumar and Patel, 2007; Martorana et al., 2010, Martorana and Koch, 2014). Post mortem studies revealed marked loss of DA receptors in the temporal and frontal lobes of Alzheimer's disease brains (Itoh et al., 1996; Kemppainen et al., 2003; Kumar and Patel., 2007; Martorana et al., 2010), regions classically involved in cognitive decline. Interestingly, most of changes regarding DA receptors, particularly D2 subtype, were found to be largely reduced at rostral and mid-levels of the temporal cortex, indicating that regions classically affected by Alzheimer's disease pathology are also sensitive to the loss of D2 receptors (Goldsmith et al., 1996; Joyce et al., 1993, 1998a; Ryoo et al., 1994). These dopamine D2/D3 receptors may play an important role in the reciprocal activity of large groups of neurons in the high-order association cortical regions, and may promote the cognitive and behavioural impairments observed in Alzheimer's disease (Joyce et al., 1998b). D2 receptor binding was significantly reduced in the striatum of Alzheimer's disease patients, even in the absence of overt extra-pyramidal symptoms (Pizzolato et al., 1996). Kemppainen and colleagues (2003) reported that D2 receptor binding potentials are reduced in the hippocampus by 30% in

Alzheimer's disease patients as compared to controls. This reduction was found to be associated with both cognitive (Kemppainen et al., 2003) and behavioral abnormalities in Alzheimer's disease patients (Tanaka et al., 2003). Localization studies of dopamine receptors in Alzheimer's disease brains have shown a preferential reduction of D2-like receptors in the hippocampus and prefrontal cortex (Kemppainen et al., 2003; Kumar and Patel, 2007). Prolonged exposure to Aβ would progressively impair the physiological release of glutamate and of GABA reducing the possibility of DA release in prefrontal cortex and hippocampus, contributing to the impairment of attention, memory, and executive functions. Our group performed a series of neurophysiological studies using transcranial magnetic stimulation (TMS) in order to investigate possible modulatory effects of DA on cortical synaptic transmission and plasticity in AD. We first demonstrated that cholinergic transmission, as measured by short-latency afferent inhibition (SLAI) TMS protocol (Di Lazzaro et al., 2002), can be transiently restored by the acute administration of a single dose of l-dopa (Martorana et al., 2009). Similar findings can be obtained by applying transdermal patches of rotigotine, which is a DA D2/D3-agonist (Martorana et al., 2013). Moreover, we discovered that that treatment with dopamine agonist rotigotine restored the altered mechanism of LTP-like cortical plasticity in Alzheimer's disease patients (Koch et al., 2012; Koch et al., 2014). Crucially, this study revealed that DA agonists seem to have some positive effects on general cognitive functions (as shown by an increase of the MMSE) and more specifically on frontal executive functions (as revealed by increased scores in the FAB), paving the way to clinical trial based on dopaminergic therapy. This hypothesis finds support on recent experimental studies showing that in animal models AD dopamine agonists may improve memory and even reduce intraneuronal amyloid deposition (Guzmán-Ramos et al., 2012; Himeno et al., 2011). The current project has the ambition to provide first time evidence that dopaminergic stimulation may have a clinical impact in patients with mild AD. Neurophysiological investigations will allow us to identify quantifiable biomarkers underlying the effects induced by dopamine agonist on the neurodegenerative brain. The application of recent neurophysiological tools, such as the combined use of transcranial magnetic stimulation

216

217

218

219

220

221

222

223

224

225

226

227

228

229

230

231

232

233

234

235

236

237

238

239

240

(TMS) during electroencephalography (EEG) will allow us to understand how dopamine agonists are able to modulate the cortical activity of the prefrontal cortex in AD patients (Kähkönen et al., 2005; Julkunen et al., 2008), likely trough DA terminals originating from the ventral tegmental nucleus, defining the neurophysiological biomarkers of clinical improvement.

SECTION 5: OBJECTIVES

The study is designed to evaluate the efficacy, safety, and tolerability of transdermal patch of Rotigotine (RTG) 4mg versus placebo (PLC) as add-on therapy with AChEI in patients with mild AD according to the consensus diagnostic criteria and MMSE score of ≥18 and ≤26 at screening. Additionally, the study aimed to test if RTG induced change in brain physiology. To this aim, we used a multimodal neurophysiological tool, such as transcranial magnetic stimulation combined with electroencephalography (TMS/EEG), to measure changes in cortical activity in the prefrontal cortex. We expected that Rotigotine could represent a valid treatment for cognitive dysfunction in AD patients, slowing the cognitive and functional decline and increasing cortical activity of the prefrontal cortex.

5.1. Primary Objective

The primary objective of this study is to test the hypothesis that therapy with Rotigotine could have a relevant clinical impact on cognitive impairment in Alzheimer's disease patients as compared with placebo. The primary objective will be evaluated using a study endpoint at 24 weeks after initiation of treatment. The primary objective will be assessed using a Generalized Linear Mixed Model (GLMM) for repeated measures on the primary outcome: Alzheimer's Disease Assessment Scale-Cognitive (ADAS-Cog), in which the specific hypothesis is that the cognitive decline at the end of the treatment phase for RTG will be significantly less than that for placebo.

5.2. Secondary Objective

The secondary objectives of this study are as follows:

- To test the hypothesis that RTG will slow the rate of decline associated with AD in the activities of daily living, as assessed with the Alzheimer's disease Cooperative Study Activities of Daily Living (ADCS-ADL), using a GLMM for repeated measures.
 - To assess benefit of treatment with RTG on frontal cognitive functions, as demonstrated through the Frontal assessment battery (FAB), using a GLMM for repeated measures.
 - To evaluate efficacy of treatment with RTG on behavior, as demonstrated through the Neuropsychiatric Inventory (NPI), using a GLMM for repeated measures.
- To provide evidence that RTG modulates the frontal cortical activity, as evaluated in terms
 of cortical excitability and oscillatory activity evoked by single-pulse TMS during EEG,
 using a repeated-measures ANOVA. These biomarkers will be collected only in subsets of
 patients.

SECTION 6: INVESTIGATIONAL PLAN

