- al., 2005; Julkunen et al., 2008). We employ TMS-evoked cortical responses (i.e., TEPs) as a novel
- 520 probe of dopamine-agonist induced cortical excitability changes. As biomarkers we will measure
- 521 neurophysiological changes induced by dopamine-agonist over the left dorsolateral prefrontal

cortex (PFC), and over the left posterior parietal cortex (I-PPC), by evaluating the cortical excitability and oscillatory activity evoked by single-pulse TMS during EEG recordings. We chose to stimulate the left DLPFC since we want to assess the spatial specificity of our treatment, whereas the left PPC is chosen as a control site. Two sets of outcome measures will be obtained assessing cortical excitability (global mean field power-GMFP) and cortical oscillatory activity.

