2.3 Statistical and Analytical Plans

2.3.1. General Considerations

Unless otherwise noted, all tests of treatment effects will be conducted at a 2-sided alpha level of 0.05; 2-sided confidence intervals will be displayed with a 95% confidence level. All tests of interactions between treatment and other factors will be conducted at an alpha level of 0.05. All analyses will follow the intent-to-treat (ITT) principle unless otherwise specified. An ITT analysis is an analysis of data by the groups to which subjects are assigned by random allocation, even if the subject does not take the assigned treatment, does not receive the correct treatment, or otherwise does not follow the protocol.

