by means of Shapiro-Wilks' test. The sphericity of the data will be tested with Mauchly's test; when sphericity is violated (i.e. Mauchly's test < 0.05) the Greenhouse–Geisser correction will be used. Pairwise comparisons will be corrected by the Bonferroni method. Safety analyses for the treatment period will include comparisons between rotigotine and placebo groups by 2-sided 0.05 significance level Chi-square tests. Statistical analyses will be performed with IBM SPSS statistics, version 24.0 and R software; significance alpha level test is set up at 0.05.

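### Four secondary objectives are worded as tests or demonstrations, each at two-sided 0.05, with no order, gate on ADAS-Cog, adjustment across endpoints or exploratory label

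*Combined protocol and SAP*

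**What the plan says.** Protocol 5.2 lists four secondary objectives:

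- ADCS-ADL: "To test the hypothesis that RTG will slow the rate of decline associated with AD in the activities of daily living".
- FAB: "To assess benefit of treatment with RTG on frontal cognitive functions, as demonstrated through the Frontal assessment battery (FAB").
- NPI: "To evaluate efficacy of treatment with RTG on behavior, as demonstrated through the Neuropsychiatric Inventory (NPI").
- TMS-EEG: "To provide evidence that RTG modulates the frontal cortical activity".

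Protocol 9.2 adds for TMS-EEG: "Two sets of outcome measures will be obtained assessing cortical excitability (global mean field power-GMFP) and cortical oscillatory activity".

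On error rates, SAP 2.3.1 says that, unless noted otherwise, "all tests of treatment effects will be conducted at a 2-sided alpha level of 0.05". SAP 2.3.4 repeats it: "significance alpha level test is set up at 0.05". The only multiplicity rule is in SAP 2.3.4: "Pairwise comparisons will be corrected by the Bonferroni method". It directly follows the ANOVA and sphericity text.

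Protocol 5.1 and 9.1 name one primary outcome, ADAS-Cog. Two other places blur this. Protocol 6.1 includes functional as well as cognitive decline in the primary hypothesis, and SAP 2.3.2 speaks of co-primary measures in the plural.

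**The concern.** The plan announces inferential claims on function, frontal cognition, behaviour and cortical activity, and gives each one the full per-test alpha. It does not say what a significant secondary means when ADAS-Cog is not significant. The Bonferroni sentence does not fill the gap. With two groups and two assessments (Protocol 6.2 and 6.4), each clinical scale has a single group-by-time test, and correcting pairwise comparisons inside one model does nothing across endpoints.

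The situation is a realistic one. SAP 2.1 sizes the trial on FAB and MMSE changes from the pilot study, not on ADAS-Cog, so FAB is a secondary for which the plan itself cites an effect and a power. If ADAS-Cog is null and FAB, say, reaches p<0.05, nothing in the plan prevents the result from being presented as demonstrated benefit.

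**Working it through.** **The plan's own figures.** The documents give no family-wise rate for the secondaries, only 0.05 per test. The one related calculation is the sample size in SAP 2.1 (paired t-test, two-sided 0.05, pre-post correlation 0.7):

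- FAB effect: (12.32 − 10.85) / √(4.43² + 4.48² − 2×0.7×4.43×4.48) = 1.47 / 3.45 = 0.426. The plan uses 0.42.
- Power at n=46 by the noncentral t distribution: 0.796 for FAB (effect 0.42) and 0.890 for MMSE (effect 0.48). The stated 0.8 and 0.9 are reproduced to rounding.

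The 0.7 is a pre-post correlation within one scale. It says nothing about correlation between endpoints, so that has to be assumed. The range used here is 0 to 0.8.

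**Chance of at least one p<0.05 when all secondary nulls are true.** For k independent tests this is 1 − 0.95^k:

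- k=3 (ADCS-ADL, FAB, NPI): 1 − 0.857 = 14.3%
- k=4 (with TMS-EEG counted once): 1 − 0.815 = 18.5%

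With equicorrelated normal test statistics (simulation, 2,000,000 draws):

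| Correlation | 3 clinical scales | 4 tests |
|---|---|---|
| 0 | 14.3% | 18.5% |
| 0.3 | 13.6% | 17.4% |
| 0.5 | 12.6% | 15.6% |
| 0.7 | 10.9% | 13.0% |
| 0.8 | 9.8% | 11.4% |

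Counting TMS-EEG once is a low count, because Protocol 9.2 names two outcome sets. Five tests give 1 − 0.95⁵ = 22.6% if independent and 18.2% at correlation 0.5.

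**Chance of the damaging scenario.** This is a false result in favour of rotigotine on at least one of the three clinical scales, together with a non-significant ADAS-Cog, when all four nulls are true. If the tests are independent it is 0.95 × (1 − 0.975³) = 0.95 × 0.0731 = 6.9%. By simulation it is 6.2% at correlation 0.3, 5.3% at 0.5, 4.0% at 0.7 and 3.2% at 0.8.

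**Effect of control.** Bonferroni at 0.05/4 = 0.0125 gives 1 − 0.9875⁴ = 4.9% if independent and at most 5% under any correlation. Holm keeps the same 5% bound. Power for FAB on the plan's own paired-test inputs (0.42, n=46) falls from 0.796 at 0.05 to 0.600 at 0.0125.

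**The case against.** The strongest reply is that this is a phase IIa trial with one named primary. The other measures are already called secondary, and unadjusted secondary tests are common at this stage. The plan sets a per-test alpha and promises no family-wise rate, so 5% across the family is an outside benchmark. Only one objective speaks of testing a hypothesis; for FAB and NPI, the demonstration wording can be read as simply naming the instrument.

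Much of this stands. Strict control of the secondaries is not obligatory here, and the wording is not uniformly confirmatory. What remains is that a reader cannot tell from the plan whether a lone significant secondary is a finding or a lead. The word secondary does not settle that when one objective is a hypothesis test and two refer to demonstration.

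A reader might also infer that the false-claim rate is 13-16% where the plan promises 5%, or about three times alpha. The documents do not support that. Those figures need an assumed correlation of about 0.5 to 0.7 for four tests, and no such value is given. TMS-EEG is collected only in subsets of patients, so giving it the same correlation as the clinical scales is a further assumption. The figures also count results favouring placebo. In four-test form they include TMS-EEG, so they overstate the risk of a false clinical benefit after a null primary.

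**Conclusion.** The structural point holds: inferential wording, a full two-sided 0.05 for each objective, and neither error control nor a supportive label. If all secondary nulls are true, the chance of at least one p<0.05 is about 11-19% for four tests and 10-14% for the three clinical scales. A false favourable result on those scales with a non-significant ADAS-Cog has a chance of about 3-7%.

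These ranges assume a common correlation between 0 and 0.8 and that each test holds its nominal level. The Poisson model for NPI might not hold it if scores are overdispersed, which the SAP does not address. The plan does not breach an error rate it stated. The defect is that it leaves open what the trial may conclude from a secondary result, and this should be settled before unblinding.

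**What to change.** First, settle the primary. Reconcile the co-primary wording in SAP 2.3.2 and the functional decline in the primary hypothesis of Protocol 6.1 with the single primary outcome in Protocol 5.1. ADCS-ADL cannot be placed in any hierarchy until this is done.

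Then, before unblinding, add to SAP 2.3.1 and 2.3.4:

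- The efficacy conclusion rests on the ADAS-Cog group-by-time test alone.
- Secondary endpoints are reported as estimates with 95% confidence intervals and unadjusted p-values, labelled supportive or exploratory.

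Reword Protocol 5.2 to match.

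If the sponsor wants a confirmatory secondary claim, specify a fixed sequence or Holm at 0.05, entered only after a significant ADAS-Cog result. A gate alone is not enough. With an assumed 80% power on ADAS-Cog and four true, independent secondary nulls, 0.80 × 18.5% = about 15% would remain.

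The supportive-label route costs only wording, with no new data or patients. Its price is that a lone secondary at p<0.05 can no longer be claimed as demonstrated. If Holm is chosen, power for FAB on the plan's own paired-test inputs drops from about 80% to 60% at the first-step alpha of 0.0125.
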